10.2 Appendix 2: Clinical Laboratory Tests

- All study-required laboratory assessments as detailed in [Table 2](#) and the laboratory manual will be performed by a local laboratory, and confirmation of review of the results must be entered into the electronic case report form (eCRF).
- Protocol-specific requirements for inclusion or exclusion of subjects are detailed in [Section 5](#) of the protocol.
- Additional tests may be performed at any time during the study as determined necessary by the investigator or required by local regulations.

Table 2. Protocol-required Laboratory Assessments

Central Laboratory Hematology	Central Laboratory Clinical Chemistry	Central Laboratory Urinalysis
Complete blood count (CBC) with differential	Chemistry panel (includes liver function tests)	Dipstick urinalysis Microscopic examination (if blood or protein is abnormal)
Other Screening Tests	Follicle stimulating hormone (as needed to confirm menopausal status for women of nonchildbearing potential only). Highly sensitive urine human chorionic gonadotropin (hCG) urine pregnancy test (as needed for women of childbearing potential). ^a	
All study-required laboratory assessments will be performed by a local laboratory.		

eCRF = electronic case report form.

^aLocal urine testing will be standard for the protocol unless serum testing is required by local regulation or IRB.

Investigators must document their review of each laboratory safety report.

10.3 Appendix 3: Adverse Events: Definitions and Procedures for Recording, Evaluating, Follow-up, and Reporting

10.3.1 Definition of Adverse Event

Adverse Event Definition

- An adverse event (AE) is any untoward medical occurrence in a subject or clinical study subject, temporally associated with the use of study intervention, whether or not considered related to the study intervention.
- NOTE: An AE can therefore be any unfavorable and unintended sign (including an abnormal laboratory finding), symptom, or disease (new or exacerbated) temporally associated with the use of study intervention.

Events Meeting the AE Definition

- Any abnormal laboratory test results (hematology, clinical chemistry, or urinalysis) or other safety assessments (eg, electrocardiogram [ECG], radiology scans, vital sign measurements), including those that worsen from baseline, considered clinically significant in the medical and scientific judgment of the investigator (ie, not related to progression of underlying disease).
- Exacerbation of a chronic or intermittent pre-existing condition including either an increase in frequency and/or intensity of the condition.
- Any new condition detected or diagnosed after study intervention administration even though it may have been present before the start of the study.
- Signs, symptoms, or the clinical sequelae of a suspected drug-drug interaction.
- Signs, symptoms, or the clinical sequelae of a suspected overdose of either study intervention or a concomitant medication. Overdose per se will not be reported as an AE/serious adverse event (SAE) unless it is an intentional overdose taken with possible suicidal/self-harming intent. Such overdoses should be reported regardless of sequelae.
- “Lack of efficacy” or “failure of expected pharmacological action” per se will not be reported as an AE or SAE. Such instances will be captured in the efficacy assessments. However, the signs, symptoms, and/or clinical sequelae resulting from lack of efficacy will be reported as an AE or SAE if they fulfill the definition of an AE or SAE.

Events NOT Meeting the AE Definition

- Any clinically significant abnormal laboratory findings or other abnormal safety assessments that are associated with the underlying disease, unless judged by the investigator to be more severe than expected for the subject’s condition.
- The disease/disorder being studied or expected progression, signs, or symptoms of the disease/disorder being studied, unless more severe than expected for the subject’s condition.

- Medical or surgical procedure (eg, endoscopy, appendectomy): the condition that leads to the procedure is the AE.
- Situations in which an untoward medical occurrence did not occur (social and/or convenience admission to a hospital).
- Anticipated day-to-day fluctuations of pre-existing disease(s) or condition(s) present or detected at the start of the study that do not worsen.

10.3.2 Definition of Serious Adverse Event

If an event is not an AE per definition above, then it cannot be an SAE even if serious conditions are met (eg, hospitalization for signs/symptoms of the disease under study, death due to progression of disease).

An SAE is defined as any untoward medical occurrence that, at any dose:
a. Results in death
b. Immediately life threatening The term 'life threatening' in the definition of 'serious' refers to an event in which the subject was at risk of death at the time of the event. It does not refer to an event that hypothetically might have caused death if it were more severe.
c. Requires inpatient hospitalization or prolongation of existing hospitalization In general, hospitalization signifies that the subject has been detained (usually involving at least an overnight stay) at the hospital or emergency ward for observation and/or treatment that would not have been appropriate in the physician's office or outpatient setting. Complications that occur during hospitalization are AEs. If a complication prolongs hospitalization or fulfills any other serious criteria, the event is serious. When in doubt as to whether "hospitalization" occurred or was necessary, the AE should be considered serious. Hospitalization for elective treatment of a pre-existing condition that did not worsen from baseline is not considered an AE.
d. Results in persistent disability/incapacity 
• The term disability means a substantial disruption of a person's ability to conduct normal life functions.• This definition is not intended to include experiences of relatively minor medical significance such as uncomplicated headache, nausea, vomiting, diarrhea, influenza, and accidental trauma (eg, sprained ankle) that may interfere with or prevent everyday life functions but do not constitute a substantial disruption.
e. Is a congenital anomaly/birth defect
f. Other medically important serious event: Medical or scientific judgment should be exercised in deciding whether SAE reporting is appropriate in other situations such as important medical events that may not be

immediately life threatening or result in death or hospitalization but may jeopardize the subject or may require medical or surgical intervention to prevent one of the other outcomes listed in the above definition. These events should usually be considered serious. Examples of such events include invasive or malignant cancers, intensive treatment in an emergency room or at home for allergic bronchospasm, blood dyscrasias or convulsions that do not result in hospitalization, or development of drug dependency or drug abuse.

10.3.3 Recording and Follow-Up of Adverse Events and/or Serious Adverse Events

AE and SAE Recording

- When an AE/SAE occurs, it is the responsibility of the investigator to review all documentation (eg, hospital progress notes, laboratory reports, and diagnostics reports) related to the event.
- The investigator will then record all relevant AE/SAE information in the electronic case report form (eCRF).
- It is **not** acceptable for the investigator to send photocopies of the subject's medical records in lieu of completion of the AE/SAE eCRF page.
- There may be instances when copies of medical records for certain cases are requested by sponsor. In this case, all subject identifiers, with the exception of the subject number, will be redacted on the copies of the medical records before submission to sponsor.
- The investigator will attempt to establish a diagnosis of the event based on signs, symptoms, and/or other clinical information. Whenever possible, the diagnosis (not the individual signs/symptoms) will be documented as the AE/SAE.
- The investigator must assign the following AE attributes:
 - AE diagnosis or syndrome(s), if known (if not known, signs or symptoms).
 - Dates of onset and resolution (if resolved).
 - Intensity (or toxicity defined below).
 - Assessment of relatedness to investigational product, other protocol-required therapies; and
 - Action taken.

Assessment of Intensity

The investigator will make an assessment of intensity for each AE and SAE reported during the study and assign it to 1 of the following categories:

- Mild: An event that is easily tolerated by the subject, causing minimal discomfort and not interfering with everyday activities.
- Moderate: An event that causes sufficient discomfort and interferes with normal everyday activities.
- Severe: An event that prevents normal everyday activities. An AE that is assessed as severe should not be confused with a SAE. Severe is a category utilized for rating the intensity of an event; and both AEs and SAEs can be assessed as severe.

An event is defined as ‘serious’ when it meets at least 1 of the predefined outcomes as described in the definition of an SAE, NOT when it is rated as severe.

Assessment of Causality

- The investigator is obligated to assess the relationship between study intervention and each occurrence of each AE/SAE. The AEs must be characterized as related or unrelated. See [Section 10.4](#) for a two-level definition of causality rating.
- A “reasonable possibility” of a relationship conveys that there are facts, evidence, and/or arguments to suggest a causal relationship, rather than that a relationship cannot be ruled out.
- The investigator will use clinical judgment to determine the relationship.
- Alternative causes, such as underlying disease(s), concomitant therapy, and other risk factors, as well as the temporal relationship of the event to study intervention administration, will be considered and investigated.
- The investigator will also consult the Investigator’s Brochure (IB) and/or Product Information, for marketed products, in his/her assessment.
- For each AE/SAE, the investigator **must** document in the medical notes that he/she has reviewed the AE/SAE and has provided an assessment of causality.
- There may be situations in which an SAE has occurred, and the investigator has minimal information to include in the initial report to sponsor. However, the sponsor suggests that the investigator assesses causality for every event before the initial transmission of the SAE data to sponsor.
- The investigator may change his/her opinion of causality in light of follow-up information and send an SAE follow-up report with the updated causality assessment.
- The causality assessment is one of the criteria used when determining regulatory reporting requirements.

Follow-up of AEs and SAEs

- The investigator is obligated to perform or arrange for the conduct of supplemental measurements and/or evaluations as medically indicated or as requested by sponsor to elucidate the nature and/or causality of the AE or SAE as fully as possible. This may include additional laboratory tests or investigations, histopathological examinations, or consultation with other health care professionals.
- If a subject dies during participation in the study or during a recognized follow-up period, the investigator will provide sponsor with a copy of any post mortem findings available including histopathology.
- New or updated information will be recorded in the originally completed eCRF.
- The investigator will submit any updated SAE data to the sponsor within 24 hours of receipt of the information.

10.3.4 Reporting of SAEs

SAE Reporting via an Electronic Data Collection Tool

- The primary mechanism for initially reporting an SAE will be the electronic data collection tool.
- If the electronic system is unavailable, then the site will use the paper SAE data collection tool in order to report the event within 24 hours.
- The site will enter the SAE data into the electronic system as soon as it becomes available.
- After the study is completed at a given site, the electronic data collection tool will be taken off-line to prevent the entry of new data or changes to existing data.
- Further details related to SAE reporting including Contact Information will be found in the Study Manual.

10.4 Appendix 4: Definition of Causality Rating

Related	A clinical event, including laboratory test abnormality, which occurs in a plausible time relationship to treatment administration and which concurrent disease or other drugs or chemicals cannot explain. The response to withdrawal of the treatment (dechallenge) ^a should be clinically plausible. The event must be definitive pharmacologically or phenomenologically, using a satisfactory rechallenge ^b procedure if necessary.
Unrelated	A clinical event, including laboratory test abnormality, with little or no temporal relationship with treatment administration. May have negative dechallenge and rechallenge information. Typically explained by extraneous factors (e.g., concomitant disease, environmental factors, or other drugs or chemicals)

^aDechallenge: Upon discontinuation of a drug suspected of causing an AE, the symptoms of the AE disappear partially or completely, within a reasonable time from drug discontinuation (positive dechallenge), or the symptoms continue despite withdrawal of the drug (negative dechallenge). Note that there are exceptions when an AE does not disappear upon discontinuation of the drug, yet drug-relatedness clearly exists (for example, as in bone marrow suppression, fixed drug eruptions, or tardive dyskinesia).

^bRechallenge: Upon re-administration of a drug suspected of causing an AE in a specific subject in the past, the AE recurs upon exposure (positive rechallenge), or the AE does not recur (negative rechallenge).

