2.3 Benefit/Risk Assessment

TER-101 was safe and well tolerated when administered as a topical ointment (1.0% w/w) twice daily for up to 2 weeks to healthy volunteer subjects (n=8) and patients (n=28) with moderate to severe AD. The most common treatment emergent adverse events (TEAEs) in TER-101 treated subjects were local application site events including pruritus, dry skin, and dermatitis. The majority of reported TEAEs in healthy volunteers or subjects with AD were mild to moderate in

severity. Three of 10 subjects with moderate to severe AD randomized to the vehicle arm withdrew due to TEAEs related to lack of efficacy. No healthy volunteers or subjects with AD treated with TER-101 withdrew from the study. There were no clinically significant safety concerns identified in vital signs, physical examinations, electrocardiograms (ECGs), or clinical laboratory assessments.

In this small study, there was no statistically significant difference in the primary efficacy analysis (percentage change from baseline in Eczema Area and Severity Index [EASI] score at Week 2) or in a sensitivity analysis using multiple imputation, between the TER-101 and placebo groups. In the sensitivity analysis using last observation carried forward, there was evidence of a trend towards a larger decrease in EASI scores and other efficacy assessments in the TER-101 compared with the placebo group. This result was also supported by the worst-case imputation sensitivity analysis. Three patients in the TER-101 group were assessed as EASI-75 (75% reduction in EASI score from baseline) responders. No patients in the placebo group met this definition. A trend towards greater improvement in the TER-101 group was also evident in the Patient Global Impression of Change assessment.

Teres Bio anticipates the most likely TEAE in the Phase 2 upcoming study will be local application site TEAEs including pruritus, dry skin, stinging/burning, pain, or dermatitis including atopic dermatitis. The protocol includes rules for treatment cessation in the event that subjects develop severe local TEAEs or high scores on the tolerability assessments. Once local AEs have abated, treatment may be re-initiated once daily. Teres Bio believes that the accrued clinical safety and preliminary efficacy data support a favorable benefit-risk profile for the proposed protocol and that appropriate monitoring and stopping rules have been included in the planned study design.

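### The two-level causality scale in Protocol 10.4 leaves a gap for plausibly timed events that atopic dermatitis could also explain, and it is not reconciled with 10.3.3

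*Protocol*

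**What the plan says.** **The rating is a forced choice.** Protocol 10.3.3 states: "The AEs must be characterized as related or unrelated". It names Section 10.4 as the place where the two levels are defined.

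**Related (Protocol 10.4).** Timing must be plausible, and the event must be one "which concurrent disease or other drugs or chemicals cannot explain". The response to withdrawal should be clinically plausible. A further sentence sets the degree of certainty: "The event must be definitive pharmacologically or phenomenologically", with rechallenge where needed.

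**Unrelated (Protocol 10.4).** This is an event "with little or no temporal relationship with treatment administration". The remaining elements are hedged. Dechallenge and rechallenge information may be negative, and the event is "Typically explained by extraneous factors", with concomitant disease among the examples.

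**A second standard (Protocol 10.3.3).** The same section that points to 10.4 also explains the phrase reasonable possibility. It "conveys that there are facts, evidence, and/or arguments to suggest a causal relationship, rather than that a relationship cannot be ruled out". The phrase does not appear in the 10.4 table.

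**Expected events (Protocol 2.3).** The most common events on the 1% ointment were "local application site events including pruritus, dry skin, and dermatitis". The sponsor anticipates similar local events in this study, with stinging or burning, pain and AD itself added to the list.

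**Use of the rating.** SAP 3.7.3 reports the incidence of treatment-related TEAEs and TESAEs in its overview, and related TEAEs again by SOC and PT. It does not redefine relatedness. Protocol 10.3.3 makes the rating one input to regulatory reporting. Under Protocol 8.4.1, reporting of SAEs after the 30-day period depends on it.

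**The concern.** A two-level scale works only if every event falls on one side. Here both definitions are written as extremes: near-certain causation on one side, and little link in time on the other. What lies between is the ordinary case in this trial. Ointment goes on AD skin twice daily, and the local reactions to be expected look much like the disease. If the rater has no clear category for these events, the related-event tables reflect how each of about 12 sites resolved the wording as well as what happened to the subjects. The study tests a higher concentration than before, so a reader will look at those tables.

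**Working it through.** No figure in the plan bears on this point, so the check is to apply the two 10.4 definitions literally.

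**Step 1: cross timing with alternative explanation.**

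| Timing plausible? | Could AD or another cause explain it? | Related? | Unrelated? |
|---|---|---|---|
| No | Yes | No | Yes |
| No | No | No | Yes, on timing |
| Yes | No | Yes, if also definitive | No, on timing |
| Yes | Yes | No | Not on timing; only the hedged extraneous-cause element fits |

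The last row is the gap. The third row has a smaller one: an event with no alternative cause that still falls short of definitive.

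**Step 2: place the expected events.** Protocol 10.5 lists pruritus and chronic dermatitis among the major diagnostic features of AD and xerosis among the minor ones. Study drug is applied twice daily to affected skin (Protocol 4.1.3), so timing will nearly always be plausible. Application-site pruritus, dry skin and dermatitis therefore fall in the last row. Stinging or burning straight after application is different: AD need not explain it, and it could qualify as Related.

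**Step 3: ask whether dechallenge evidence will settle it.** Protocol 6.2 holds treatment by rule only for severe local effects or a high tolerability score. Milder events will rarely produce withdrawal or rechallenge evidence.

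**Step 4: compare the two standards.** Under 10.3.3, evidence or argument suggesting causation is enough for a reasonable possibility, and AD as a contributor does not rule it out. Under 10.4, AD as a sufficient explanation does rule out Related. The same event can pass one and fail the other.

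**Step 5: direction.** The choice is forced, Related carries a definitive bar, and concomitant disease is named under Unrelated. Doubtful events are therefore more likely to go to Unrelated.

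**Illustration on assumed values only.** The documents give no event rates.

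- n = 60 / 2 = 30 subjects on TER-101 (Protocol 9.2, randomized 1:1).
- p = assumed share with an application-site event that meets the reasonable-possibility standard, 10% to 30%.
- f = assumed share of those who also meet 10.4 literally, 0% to 100%. The rest are taken to be rated Unrelated.
- Counted under reasonable possibility: n × p = 3, 6 or 9 at p = 10%, 20% or 30%.
- Counted under 10.4: n × p × f. At p = 20% and f = 25%, 30 × 0.20 × 0.25 = 1.5, against 6.
- Chance that no subject is counted in that case: (1 − 0.05)^30 = 0.21.
- At f = 50%, the 10.4 count runs from 1.5 (p = 10%) to 4.5 (p = 30%). At f = 0 it is zero. At f = 100% nothing is lost.

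The range runs from no loss to total loss. It shows what the wording could do and does not estimate what it will do.

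**The case against.** Several arguments on the other side have force.

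- **No event goes unrated.** The choice is forced, and 10.3.3 tells the investigator to use clinical judgment and to weigh underlying disease, timing and the Investigator's Brochure. Some sites may apply the lower standard. A reader might infer that related events will certainly be undercounted. The documents do not support that; they support inconsistent rating, probably skewed low.
- **Unrelated can be stretched.** Its extraneous-cause element names concomitant disease, so an AD-explained event can be placed there, although the timing element fits badly. A reader might also infer that all expected application-site events lack a category. Immediate stinging or burning is a counterexample.
- **Other rules narrow the affected events.** Protocol 10.3.1 excludes expected signs of the disease under study from adverse events unless they are more severe than expected for the subject. Protocol 8.4 has skin events flagged in the eCRF for underlying condition and for application site. This helps, but the flag is not the causality rating, and SAP 3.7.3 specifies no table by it.
- **Tolerability does not use this rating.** A reader might infer that the tolerability objective is compromised. That endpoint is the set of 0 to 3 grades for erythema, burning/stinging and pruritus, tabulated under SAP 3.7.2. All-causality TEAEs are also unaffected, and the blinded comparison with vehicle remains available. Nothing in the documents suggests that similar events would be rated differently by arm.
- **Safety reporting is largely protected.** A reader might infer that expedited reporting is weakened across the board. Under Protocol 8.4.1, all SAEs go to the sponsor within 24 hours, and events within 30 days of the last dose are reported whatever their cause. What remains exposed is later SAEs and regulatory reports that depend on causality. The events at issue would seldom be serious.
- **The conflict may be looser than it seems.** Section 10.3.3 explains reasonable possibility but never says that it is the test for Related; it assigns that role to 10.4. That is fair. It leaves an unreconciled phrase beside a strict table, and the gap in the table exists whatever 10.3.3 says.

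**Conclusion.** The point holds within limits. The 10.4 scale does not cover every case, and neither document reconciles it with 10.3.3 or closes the gap. Plausibly timed events that AD could also explain may be rated differently from site to site, and probably too often as Unrelated. The consequence is confined to the treatment-related TEAE and TESAE summaries and to causality-dependent reporting. The size cannot be estimated. The conclusion assumes that at least some raters follow the 10.4 table as written and that mild local events usually lack dechallenge evidence. It is worth correcting because the affected tables are planned outputs and the correction is cheap.

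**What to change.** Reword the 10.4 table to agree with 10.3.3:

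- **Related:** a reasonable possibility, meaning that facts, evidence or arguments suggest causation, even if AD may contribute.
- **Unrelated:** no reasonable possibility.

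Remove the condition that nothing else can explain the event, and the definitive and rechallenge conditions. Every event then falls in one category. Because 10.3.3 asks for more than a link that cannot be excluded, the change does not make every AD-compatible event Related. SAP 3.7.3 should cite this standard as the definition of a treatment-related TEAE.

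The cost is a short protocol amendment with site guidance, and the reported related-event rate may be somewhat higher. If events have already been rated, they should be re-rated under the blind so that one standard applies throughout. Dosing, endpoints and sample size do not change.
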